### 4.2 Interpretation of Anticipated Results:

## Statistical analysis

Means and standard deviations of participant demographic data, as well as mEQ, VAS, and other outcome scores will be calculated. Two tailed paired t tests will be used for parametric data; Wilcoxon rank sum tests will be used for non-parametric data in order to compare differences in outcome measures between the two treatment groups.

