### Randomization and Masking Procedures (Treatment vs Control; T vs C)

A computer-generated 1:1 block randomization scheme will be used to assign participants to receive either a CRFA *or* a sham procedure (wherein no RF energy is delivered after needle placement, and only local anesthetic is delivered). Randomization will be performed by the proceduralist immediately before the injection procedure by opening an opaque envelope to reveal the participant number and group assignment printed on an index card. Participants, surgeons and all other study personnel, including those who will perform follow-up evaluations, will be blinded to group assignment. One board certified, fellowship trained anesthesiologist ([name]) with 16 years of injection experience will perform all injections. [name] will not be involved in the collection of any primary or secondary data outcome.

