## Statistical Analyses:

Baseline characteristics (e.g., sociodemographic variables, primary and secondary outcomes) will be compared between treatment groups using t-tests or chi-square tests for categorical variables. We will conduct intent-to-treat (ITT) analyses for all primary and secondary outcomes

using a series of generalized mixed-effects regressions. All statistical tests will be two-sided with significance set at  $p\leq.05$ . SAS statistical software version 9.2 (SAS Institute Inc., Cary, NC, USA) will be used for statistical analyses.

In preliminary analysis, the distributional aspects of the variables under consideration will be examined through descriptive statistics. These statistics will include measures of location (mean, median, quartiles) and measures of dispersion (range, standard deviation, variance) for continuous variables and frequencies of the levels of categorical variables. These measures will also assist with a data cleaning/screening procedure to eliminate any possible copying, handling, recording or measurement errors. In addition to the features described above, the dependence of outcome measures will need to be properly accounted for in the data analysis as measures will be made at multiple times for the same participant. Consequently, these observations tend to be correlated and require statistical techniques that can properly account for the correlation in order to draw valid inference. Our general approach for analyzing these multiple types of data in this trial will be the Generalized Linear Mixed-Effect Models (GLMM).

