## Statistical Power

The power analysis for this study was performed using data from Choi et al and assumptions regarding perioperative opiate requirements in patients undergoing TKR without an indwelling epidural catheter or peripheral nerve block. A sample size of 28 per group is needed to detect a difference in analgesic use of 15 morphine equivalents (ME) per 24 hour cycle, assuming the controls use 47 ME per 24 hours cycle with a standard deviation of 19 ME with a power of .81 at alpha = 0.05. The sample size calculation was computed using a two-sided Mann-Whitney Test (PASS). To correct for lost to follow up and dropout rates, we will recruit 30 patients into each treatment group.

Duration of follow-up This trial is designed with 6-month duration of follow up after surgery.

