### 4.0 Data Analysis:

Primary outcome:

• Between-group difference in analgesic use (MQS III score) at 48 hours.

Secondary outcomes: Between groups at 48 hours, 1, 3, 6 months in:

- 1. Visual Analog Scale for pain (at rest, with mobilization or weight bearing)
- 2. Knee Society Scale (clinician); WOMAC (patient)
- 4. Physical therapy milestones
  - a. Time to active SLR
  - b. Time until patient can get out of bed
  - c. Time until patient able to ambulate < 100 feet
  - d. Time until patient able to ambulate around room > 100 feet

e. Time until patient is able to climb stairs (quantify specifics, how many steps are considered appropriate?)

- 5. Patient Global Perception of Change (GPC)
- 6. Patient Satisfaction (Likert scale)
- 6. Hospital Anxiety and Depression Score (HADI)
- 7. SF12
- 8. McGill Pain Questionnaire

9. Inpatient length of Stay (LOS; days) and Physical Therapy "clearance for discharge" (days)

- 10. Complications of the injection procedure
- 11. Medication related adverse events (i.e. sedation, nausea, pruritus, delirium)

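### Section 4.2 names paired t tests to compare two unmatched randomized arms (probably a slip for unpaired), and nothing ranks these tests against the mixed models assigned to the same outcomes

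*Combined protocol and SAP*

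**What the plan says.** Section 4.2 (Interpretation of Anticipated Results, Statistical analysis) states: "Two tailed paired t tests will be used for parametric data; Wilcoxon rank sum tests will be used for non-parametric data". The sentence goes on to give the purpose: "in order to compare differences in outcome measures between the two treatment groups".

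Other parts of the document bear on this rule:

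- **Randomization and Masking Procedures:** "A computer-generated 1:1 block randomization scheme will be used to assign participants" to C-RFA or sham. No matching is described. The paragraph on one exposure to the intervention rules out repeat injections, so there is no crossover.
- **Statistical Analyses (Section 3.0):** "We will conduct intent-to-treat (ITT) analyses for all primary and secondary outcomes", "using a series of generalized mixed-effects regressions". The section goes on to call generalized linear mixed-effects models the general approach.
- **Statistical Power:** the sample size comes from a two-sided Mann-Whitney test, which is a test for independent groups. "To correct for lost to follow up and dropout rates, we will recruit 30 patients into each treatment group".
- **Section 4.0, primary outcome:** "Between-group difference in analgesic use (MQS III score) at 48 hours".

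**The concern.** There are two separate problems.

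**The wrong test is named.** A paired t test needs a defined partner for each observation. These arms have none, so the analyst would have to invent pairs, for example by listing order, and the p-value would depend on that arbitrary order. If the arms finish with unequal numbers, the surplus patients in the larger arm have no partner and drop out of the test. That conflicts with the intent-to-treat commitment. A within-patient (before and after) reading does not rescue the sentence, because its stated purpose is the comparison between groups.

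**Two analyses cover the same outcomes without a ranking.** Section 3.0 gives all primary and secondary outcomes to mixed models. Section 4.2 gives outcome measures to t or rank sum tests and includes morphine equivalents among the scores it summarizes. It does not call these tests supportive, descriptive or a fallback, and it gives no criterion for treating data as parametric. The primary test could therefore be chosen after the data are seen. This problem remains even if *paired* is set aside as a typing error.

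**Working it through.** **Inputs (Statistical Power section).** Difference 15 ME per 24 hours, SD 19 ME, control mean 47 ME, two-sided alpha 0.05, 28 per group needed, 30 per group recruited, stated power 0.81.

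**1. The plan's own figure.** For normal data the Mann-Whitney test has efficiency 3/π relative to the t test, so the effective n is 28 × 3/π = 26.74 per group. The noncentrality is 15 / (19 × √(2/26.74)) = 2.887, with 2 × 26.74 − 2 = 51.5 df. Power is 0.8085, which reproduces 0.81. Direct simulation gives 0.800 to 0.805. The sizing therefore rests on independent groups.

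**2. Paired against unpaired t.**

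- Unpaired: noncentrality 15 / (19 × √(1/n₁ + 1/n₂)), df = n₁ + n₂ − 2.
- Arbitrary pairing of independent arms: m = min(n₁, n₂) differences, each with SD 19√2; noncentrality 15√m / (19√2), df = m − 1.

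At 28 v 28 both noncentralities equal 2.954. The only loss is in degrees of freedom (27 instead of 54). With unequal arms, discarded patients add to the loss.

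| Patients analysed | Paired | Unpaired | Loss (points) |
|---|---|---|---|
| 28 v 28 | 0.813 | 0.827 | 1.4 |
| 30 v 29 | 0.827 | 0.846 | 1.9 |
| 30 v 28 | 0.813 | 0.840 | 2.7 |
| 30 v 27 | 0.797 | 0.832 | 3.5 |
| 30 v 26 | 0.781 | 0.825 | 4.4 |

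**3. Averaging over dropout.** The plan's allowance of 30 for 28 implies a loss of 2/30 = 6.7%. Assume independent binomial loss from 30 per arm, and show 3% and 10% as a range.

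| Loss per patient | Paired | Unpaired | Arms unequal | Mean patients discarded |
|---|---|---|---|---|
| 3% | 0.821 | 0.841 | 67% | 0.97 |
| 2/30 | 0.800 | 0.826 | 79% | 1.49 |
| 10% | 0.781 | 0.811 | 83% | 1.82 |

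At 2/30 the arms differ by 1 or 2 patients in 60% of trials and by 4 or more in 6.8%.

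**4. Type I error.** This uses 200,000 simulated null trials per scenario, with normal data, mean 47 and SD 19. The unpaired t test stands in for the mixed model with treatment as the only factor and one value per patient. At 28 v 28 each test alone is sound: paired t 0.050, unpaired t 0.050, Mann-Whitney 0.047. Reporting the smallest p-value gives:

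| Patients analysed | Smaller of unpaired t and Mann-Whitney | Smallest of those two and paired t |
|---|---|---|
| 28 v 28 | 0.059 | 0.066 |
| 30 v 28 | 0.060 | 0.070 |
| 30 v 26 | 0.060 | 0.073 |

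At 28 v 28 the paired option itself adds about 0.007. With skewed (gamma) data at 28 v 28 the two figures are 0.061 and 0.068.

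**5. Dependence on listing order.** In one simulated data set with 28 per arm, the unpaired p-value was 0.083. Randomly re-pairing the same data gave paired p-values from 0.042 to 0.134 (central 95%). This is only an illustration, but it shows that listing order alone can move the result across 0.05.

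**The case against.** The strongest reply is that *paired* is a one-word slip that the rest of the plan already corrects. The nonparametric counterpart named is the rank sum test, not the signed rank test. The sizing uses Mann-Whitney, the baseline comparisons use plain t tests, and the primary outcome is called a between-group difference. No pairing variable exists, so literal execution is unlikely. This is fair: the power losses above apply only if the sentence is followed literally, and the 4-point end needs an imbalance that is uncommon at the plan's own dropout allowance.

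A second reply is that the inflated error rates come from deliberately choosing the smallest p-value, which no section prescribes. Section 4.2 ties the choice of test to whether data are parametric. Simulating that rule with a Shapiro-Wilk check per arm at 0.05 (an assumed criterion, since the plan names none; 20,000 trials, 28 v 28) gave type I error of 0.053 for normal and 0.055 for gamma data. The plain t test gave 0.052 and 0.050 in the same runs. Following Section 4.2 in good faith therefore costs little. The larger figures show how much room the missing ranking leaves, not what would be expected.

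Third, Section 3.0 comes close to a ranking, since it claims all outcomes for mixed models and calls them the general approach. It does have the stronger claim to the primary outcome. Even so, neither section refers to the other's tests, so the ranking has to be inferred.

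These replies limit the weight of the point. They do not make the sentence correct or identify the primary test.

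**Conclusion.** Both parts hold. The paired t test is wrong as written for two unmatched arms, and no section says which analysis produces the primary 48-hour p-value. The second part carries more weight, because the first is probably a slip.

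The size is small. Literal pairing leaves type I error at about 0.05 and costs 1.4 to 4.4 points of power in the cases shown, or 2.5 points averaged over a 2/30 loss. Choosing the smallest p-value would raise type I error to about 0.059 with two tests and to 0.066 to 0.073 with three.

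These figures assume normal data, independent dropout and an unpaired t test in place of the mixed model. The plan does not specify the model's terms, so inflation from choosing between the actual mixed model and the Section 4.2 tests is not estimated. The power figures refer to ME per 24 hours, the sizing variable, whereas Section 4.0 states the primary outcome as an MQS III score. The sample size is not affected. This should be fixed before analysis.

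**What to change.** 1. In Section 4.2, replace *paired t tests* with *independent two-sample t tests*.
2. Name the single analysis that gives the primary 48-hour p-value: either the mixed model of Section 3.0, or one unpaired test such as the Mann-Whitney test used for sizing.
3. Label the remaining analyses as sensitivity analyses, and make the Statistical Analyses section and Section 4.2 agree.

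The cost is wording only. With 28 per group, power is 0.827 for the unpaired t test and about 0.805 (simulated, normal data) for Mann-Whitney, in line with the plan's 0.81. No additional patients or procedures are needed.
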